2.2 Secondary Objectives

- 2.2.1 To assess the safety profile of each of these agents in this patient population.
- 2.2.2 To assess whether the tumor response rate (as determined using the RECIST criteria) among those randomized to Z-endoxifen HCl differs from that among those randomized to tamoxifen.
- 2.2.3 To estimate the median progression-free survival time for those who receive Z-Endoxifen HCl after disease progression with tamoxifen.

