3.3 Registration Eligibility Criteria

Registration must be completed within 28 days of Pre-registration

3.3.1 Patients with either measurable disease as defined by RECIST criteria (See Section 11.0) or bone only disease are eligible. Note: Those patients with both non-measurable disease and bone metastases are eligible.

- Non-measurable bone only disease: Non-measurable bone only disease may include any of the following: blastic bone lesions, lytic bone lesions without a measurable soft-tissue component, or mixed lytic-blastic bone lesions without a measurable soft-tissue component.
- Lytic bone lesions, with an identifiable soft tissue component, evaluated by CT or MRI, can be considered as measurable lesions if the soft tissue component otherwise meets the definition of measurability previously described.

3.3.2 No tumors involving spinal cord or heart.

3.3.3 No visceral crisis, lymphangitic spread or known brain metastases: Visceral crisis is not the mere presence of visceral metastases, but implies severe organ dysfunction as assessed by symptoms and signs, laboratory studies, and rapid progression of disease.

3.3.4 Histologic confirmation, from the A011203 Pre-registration biopsy, by institutional/local pathologist of either locally advanced or metastatic breast cancer that is estrogen receptor positive and HER2 negative.

Those patients with bone only disease with either no tumor or insufficient tumor for ER/PR and HER2 staining after the bone biopsy are still eligible to participate in this study.

3.3.5 Estrogen receptor positive disease is defined as > 10% nuclear staining.

3.3.6 **HER2 Negative Disease as per 2013 ASCO/CAP guidelines, one of the following must apply:**

- 1) 0 or 1+ by IHC and not amplified by ISH
- 2) 0 or 1+ by IHC and ISH not done
- 3) 2+ by IHC and not amplified by ISH or
- 4) IHC not done and not amplified by ISH

3.3.7 **None of the following therapies are allowed prior to registration*:**

- Chemotherapy \leq 2 weeks
- Immunotherapy \leq 2 weeks
- Biologic therapy \leq 2 weeks
- Hormonal therapy \leq 2 weeks
- Monoclonal antibodies \leq 2 weeks
- Radiation therapy \leq 2 weeks
- Anti-Her-2 or other “targeted” (e.g. mTOR) therapy \leq 2 weeks

*Note: Any toxicities derived from these therapies must be \leq grade 2 prior to starting study therapy.

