11.4.4 Overall Objective Status

The overall objective status for an evaluation is determined by combining the patient’s status on target lesions, target lymph nodes, non-target lesions, non-target lymph nodes, and new disease as defined in the following tables:

For Patients with Measurable Disease

Target Lesions & Target Lymph Nodes	Non-Target Lesions & Non-Target Lymph Nodes	New Sites of Disease	Overall Objective Status
CR	CR	No	CR
CR	Non-CR/Non-PD	No	PR
PR	CR Non-CR/Non-PD	No	PR
CR/PR	Not All Evaluated*	No	PR**
SD	CR Non-CR/Non-PD Not All Evaluated*	No	SD
Not all Evaluated	CR Non-CR/Non-PD Not All Evaluated*	No	Not Evaluated (NE)
PD	Unequivocal PD CR Non-CR/Non-PD Not All Evaluated*	Yes or No	PD
CR/PR/SD/PD/Not all Evaluated	Unequivocal PD	Yes or No	PD
CR/PR/SD/PD/Not all Evaluated	CR Non-CR/Non-PD Not All Evaluated*	Yes	PD

* See Section [11.4.3.1](#)

11.4.5 For those patients with non-measurable, bone-only disease, objective progression will be established if at least 1 of the following criteria is met:

- the appearance of 1 or more new lesions (in bone or outside of bone), or
- unequivocal progression of existing bone lesions.

The finding of a new lesion should be unequivocal and not attributable to findings thought to represent something other than tumor (for example, some ‘new ributab lesions may be simply healing or flare of preexisting lesions). Pathologic fracture, new compression fracture, or complications of bone metastases will not be considered as evidence of disease progression, unless at least 1 of the above criteria is met.

11.4.6 Symptomatic Deterioration: Patients with global deterioration of health status requiring discontinuation of treatment without objective evidence of disease progression at that time, and not either related to study treatment or other medical conditions, should be reported as PD due to “symptomatic deterioration.” Every effort should be made to document the objective progression even after discontinuation of treatment due to symptomatic deterioration.

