13.0 STATISTICAL CONSIDERATIONS**13.1 Study Design**

A randomized phase II clinical trial design was chosen to assess whether Z-Endoxifen HCl shows promise in providing greater in antitumor activity (in terms of increasing progression-free survival) than tamoxifen in postmenopausal women with metastatic ER positive breast cancer that is endocrine resistant.

This study will use a dynamic allocation procedure to allocate an equal number of patients to each of the treatment arm. This procedure will balance the marginal distributions of the stratification factors between these treatment arms. The stratification factors that will be used are: prior palbociclib and/or everolimus, type of disease and degree of endocrine resistance (see Section [4.8](#)).

All patients meeting the eligibility criteria who have signed a consent form and have begun treatment will be evaluable for assessment of all of the clinical endpoints. Patients will be included in the treatment group they were randomized to regardless of their actual treatment or duration of treatment. Summary statistics for patient and tumor characteristics, eligibility rates, length of follow-up, and treatment acceptance rates will be calculated by assigned treatment arm.

13.1.2 Definition and documentation of primary endpoint.

The primary endpoint is progression-free survival (PFS) defined as the time from randomization to documentation of local, regional or distant disease progression or death without progression of disease.

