13.1.6.2 Tumor Response Rate by study arm

The tumor response rate is defined as the 100% time the number of patients with a CR or PR (as defined by the RECIST criteria) on 2 consecutive evaluations at least 6 weeks apart divided by the total number of eligible patients who began study treatment. A 90% binomial confidence interval will be constructed for the true response rate.

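### The tumor response rate is planned only over all eligible treated patients; a rate in patients with measurable disease should be reported beside it and lead

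*Combined protocol and SAP*

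**What the plan says.** Objective 2.2.2 compares response between arms: "To assess whether the tumor response rate (as determined using the RECIST criteria) among those randomized to Z-endoxifen HCl differs" from that on tamoxifen. Section 13.1.6.2 builds the numerator from "the number of patients with a CR or PR (as defined by the RECIST criteria) on 2 consecutive evaluations at least 6 weeks apart", and the count is then "divided by the total number of eligible patients who began study treatment". On precision it says only this: "A 90% binomial confidence interval will be constructed for the true response rate". It names no between-arm test, expected response rate or power. Section 13.1 sets the same population throughout: patients who are eligible, have consented and "have begun treatment will be evaluable for assessment of all of the clinical endpoints".

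On who is in that population, section 3.3.1 states: "Patients with either measurable disease as defined by RECIST criteria (See Section 11.0) or bone only disease are eligible". Its note adds patients with both non-measurable disease and bone metastases. Section 4.8 stratifies by disease type with two levels, measurable and bone only.

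On how response is scored, PR in 11.4.3.2 needs a fall of at least 30% in the sum of target-lesion dimensions. The overall-status table in 11.4.4 is headed for measurable disease. Section 11.4.5 addresses the bone-only group, but only for progression: "For those patients with non-measurable, bone-only disease, objective progression will be established if at least 1 of the following criteria is met".

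**The concern.** The numerator can be reached, in practice, only by patients with something to measure, while the denominator also holds patients who have nothing to measure. The planned figure therefore mixes drug activity with the case mix of enrolment. It cannot be set beside response rates from measurable disease, and the 90% interval describes a quantity that would change if more or fewer bone-only patients were enrolled. No measurable-disease rate is planned from which a reader could recover the other quantity. Objective 2.2.2 would then be answered on a scale that understates both the rate and the absolute difference among patients who can be assessed for response.

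The exploratory marker analyses in 13.2.2 and 13.2.4 also use response and state no denominator of their own, so they may inherit this one.

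**Working it through.** **The plan's own figure.** The documents give no figure for response. The primary design does reproduce: with hazard ratio 0.50, one-sided alpha 0.10 and 95% log-rank power (13.1.3), the Schoenfeld formula gives 4 x (1.2816 + 1.6449)² / (ln 0.5)² = 71.3, rounded up to the stated 72 events. It does not depend on this point.

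**Inputs.** 40 patients per arm (13.1.3); 90% interval (13.1.6.2). Assumed, because the documents do not give them: the non-measurable share b, and the response rates in measurable disease.

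**Step 1, the rate.** Let p be the response rate in measurable disease and c the rate of complete disappearance in non-measurable disease. Then

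reported rate = (1-b) x p + b x c.

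With c = 0 and p = 20%: 0.8 x 20 = 16% at b = 20%; 0.7 x 20 = 14% at 30%; 0.6 x 20 = 12% at 40%.

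If non-target CRs were counted, at an assumed c of 2% to 5% and b = 30%: 14.0 + 0.6 = 14.6% up to 14.0 + 1.5 = 15.5%. This is still well below 20%.

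**Step 2, the comparison.** With b equal in both arms and c = 0, the difference is multiplied by (1-b) and the ratio is unchanged. Illustration with 5% versus 20% in measurable disease (difference 15 points, ratio 4.0, odds ratio 4.75):

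| b | Reported rates | Difference (points) | Rate ratio | Odds ratio | Power, all treated (40 per arm) | Power, measurable only |
|---|---|---|---|---|---|---|
| 20% | 4.0% v 16.0% | 12.0 | 4.0 | 4.57 | 55.8% | 56.9% (32 per arm) |
| 30% | 3.5% v 14.0% | 10.5 | 4.0 | 4.49 | 50.7% | 52.1% (28 per arm) |
| 40% | 3.0% v 12.0% | 9.0 | 4.0 | 4.41 | 45.3% | 47.0% (24 per arm) |

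Power is for a two-sided 10% comparison, chosen only for illustration. With 10% versus 30% at b = 40% it is 50.3% against 53.6%. The absolute scale is diluted; the relative scale and power hardly move.

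**Step 3, unequal shares.** If b were 25% in one arm and 35% in the other, with a 20% rate in measurable disease in both, the reported rates would be 0.75 x 20 = 15.0% and 0.65 x 20 = 13.0%. That is a 2-point difference with no drug effect. Stratification by disease type limits this.

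**Step 4, the interval.** Six responders in an arm, exact (Clopper-Pearson) 90% limits:

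| Denominator | Rate | 90% interval | Width (points) |
|---|---|---|---|
| 40 (as planned) | 15.0% | 6.7 to 27.5 | 20.8 |
| 32 (b = 20%) | 18.8% | 8.5 to 33.7 | 25.2 |
| 28 (b = 30%) | 21.4% | 9.8 to 38.0 | 28.2 |
| 24 (b = 40%) | 25.0% | 11.5 to 43.5 | 32.0 |

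The width grows by 25.2/20.8 = 1.21 to 32.0/20.8 = 1.54, that is by 21% to 54%. Much of this is rescaling, since the responders are the same six.

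**The case against.** The denominator is stated openly, agrees with section 13.1, and is conservative. It estimates response across everyone enrolled and treated, which is a legitimate quantity, and stratification by disease type keeps the arms comparable. All of that stands. It argues for keeping the all-treated rate, but not for reporting it alone.

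A reader might infer that non-measurable patients have no response category at all and are non-responders by construction. The documents do not go that far. Section 11.4.2 classes non-measurable sites as non-target disease, and 11.4.3.3 defines a lesion-level CR for it. What is missing is an overall-status rule that applies this CR to these patients. Section 11.4.4 also refers to tables in the plural while only one is present, so a second table may have been lost in the text available. PR is closed to these patients; for CR the rule is unclear rather than shown to be absent.

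A reader might also infer that any treatment difference is understated. Only the absolute difference is: the rate ratio is preserved and power barely changes.

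The size is assumed. The one response rate cited for tamoxifen alone after an aromatase inhibitor is 0% (1.3.4), which no denominator can dilute. The difference would then equal the endoxifen rate and would still shrink by (1-b). Lytic lesions with a measurable soft-tissue component count as measurable (3.3.1, 11.2.1), so b is smaller than the share of patients with bone disease.

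Finally, it is tempting to say that a marker commoner in bone-only disease will appear to predict non-response. That is possible, but no such marker is identified. Section 13.2.3 calls the DNA analyses exploratory, and 6.2.2 expects low tissue yield from bone, so bone-only patients may be under-represented there.

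**Conclusion.** The point holds for the response rate and the absolute difference between arms. Both are reported at about (1-b) of their value in assessable patients, provided that b is similar across arms and non-target CRs are rare. At b = 20% to 40%, a 20% rate becomes 16% to 12% and a 15-point difference becomes 12 to 9 points. Neither b nor the response rates come from the documents, so these figures show the range and do not forecast the trial's result. The text does not support a claim of a biased comparison, a material loss of power, or a demonstrated error in the marker analyses. The endpoint is secondary, so this is a low-cost improvement and not a flaw in the trial's main conclusion.

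**What to change.** In 13.1.6.2, make the main response estimate, its 90% interval and the arm comparison for objective 2.2.2 those in eligible treated patients with measurable disease at baseline. Keep the all-treated rate beside it as supportive. Because measurability is fixed before treatment, the subset does not depend on outcome.

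Define measurable disease by 11.2.1 and not by the disease type factor in 4.8 alone. That factor has no explicit level for patients who have bone metastases together with other non-measurable disease. Use the same set for the response analyses in 13.2.2 and 13.2.4. A line in 11.4 stating how overall status is assigned in non-measurable disease would settle how the supportive rate treats a non-target CR.

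The cost is a few lines of text, with no new data, since baseline lesion measurements are already collected. The statistical price is the wider interval shown above: 21% to 54% wider for six responders at b = 20% to 40%.

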13.1.6.3 Overall survival distribution by study arm

Overall survival time is defined as the time from randomization to death due to any cause. The distribution of survival times will be estimated using the method of Kaplan-Meier.

13.1.7 Monitoring

The study chair, the faculty statistician and the executive officer will review the trial data every 3 months to identify accrual, toxicity, and endpoint problems that might be developing. The faculty and secondary statistician will prepare a report containing accrual, adverse events, and efficacy data which will be submitted to the ALLIANCE Data and Safety Monitoring Board on a semi-annual basis.

Safety stopping rules will be applied to each treatment arm separately. If 3 or more of the first 10 patients randomized to a given treatment arm or 30% or more of patients randomized to that treatment arm thereafter develops a grade 4 hematologic or non-hematologic toxicity possibly, probably or definitely related to treatment, the enrollment to the trial will be temporarily suspended so that all AE data can be examined. The study chair and the faculty statistician will formulate a trial recommendation to present to the ALLIANCE DSMB and CTEP for approval.

The study chair and the faculty statistician will formulate a trial recommendation to present to the ALLIANCE DSMB and CTEP for approval.

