13.1.3 Sample Size, Accrual Time and Study Duration

This trial was designed under the assumption that the median progression-free survival time among patients receiving tamoxifen is 3.0 months. Disease assessments in this trial are made at a frequency that is half the hypothesized median of the tamoxifen arm. Stone et al [41, 42] (2, 3) found that when disease assessments are made at a frequency that is half the control median, the difference in power between the log-rank test (with documented progression times) and generalized log-test with interval censored data was < 3%. As such we will determine the sample size assuming a log-rank test will be used with one-sided alpha=0.10 and power=95% so that the interval censored approach with the generalized log-rank test will have a power of > 90%.

With a sample size of 80 eligible patients (40 per treatment arm randomized in equal numbers) over a 15 month period and followed at least another 9 months after the close of enrollment before analysis is undertaken, a one-sided alpha=0.10 generalized log-rank test will have at least a 90% chance of detecting a 50% decrease in hazard of disease progression with Z-Endoxifen HCl relative to tamoxifen.

That corresponds to being able to detect an increase in the median PFS time from 3.0 months with tamoxifen to 6.0 months with Z-Endoxifen HCl.

An additional 14 patients will be screened to account for ineligible patients (tumors that are ER negative on biopsy) and those who cancel participation prior to starting treatment.

As of November 1, 2016, 24 (30%) of the 81 patients enrolled on this trial were found to have ER negative and/or HER2 positive breast cancer, a second primary cancer, or benign disease, making them ineligible. Therefore, the number of patients needed to be screened to obtain 80 eligible patients will be increased from 94 to 115 patients.

The efficacy analysis will be conducted when at least 72 patients have provided documentation of local, regional or distant disease progression or death without progression of disease.

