13.1.6 Secondary Clinical Endpoints

13.1.6.1 Adverse Events

Per CTEP Version 4.0 of the NCI CTCAE, an adverse event (AE) is any unfavorable and unintended sign (including an abnormal laboratory finding), symptom, or disease temporally associated with the use of a medical treatment or procedure that may or may not be considered related to the medical treatment or procedure. All grade 2, 3, 4 or 5 adverse events will be documented and assigned an attribute by treating clinician as to its relationship to treatment.

Note: Serious adverse events will be reported on CTEP-AERS using CTCAE v5.0.

For a given AE, the proportion of patients on each treatment arm who report developing a grade 2-5 of this AE will be determined.

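### The safety suspension rule in 13.1.7 counts grade 4 toxicities only, so a treatment-related death adds nothing to the count; its later denominator is also ambiguous.

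*Combined protocol and SAP*

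**What the plan says.** Section 13.1.7 (Monitoring) sets the only rule in the plan that commits in advance to pausing accrual for toxicity. "Safety stopping rules will be applied to each treatment arm separately". It has two parts:

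- **Early part:** "If 3 or more of the first 10 patients randomized to a given treatment arm" have a qualifying event.
- **Later part:** "or 30% or more of patients randomized to that treatment arm thereafter develops a grade 4 hematologic or non-hematologic toxicity".

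The qualifying event is the same for both: a patient who "develops a grade 4 hematologic or non-hematologic toxicity possibly, probably or definitely related to treatment". If either part is met, "the enrollment to the trial will be temporarily suspended so that all AE data can be examined", and a recommendation then goes to the DSMB and CTEP.

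The rule does not mention grade 5 or death. It gives no minimum number of patients for the later part, no checking schedule and no operating characteristics. By contrast, 13.1.6.1 says "All grade 2, 3, 4 or 5 adverse events will be documented", and the footnote on late events in 9.2.1 also names grade 4 and grade 5 individually.

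**The concern.** A suspension rule should be executable from its text, and a fatal related toxicity should weigh at least as much as a non-fatal one. Here a patient whose only qualifying event is a related death, recorded as grade 5, is not counted. Two sets of data that any safety board would rank the other way round get the wrong order: three grade 4 events pause enrolment, while two grade 4 events and a death do not.

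The second issue is reproducibility. The later part can be read as starting a fresh count at patient 11, or as the same 30% threshold carried forward over everyone in the arm. Two statisticians could act differently on identical data. On the fresh-count reading, a single event can pause the whole trial.

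**Working it through.** The plan states no operating characteristics for this rule, so there is no figure of its own to reproduce.

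**Inputs from the documents.** Thresholds of 3 of 10 and 30%, applied per arm (13.1.7). Arm size 40: "With a sample size of 80 eligible patients (40 per treatment arm randomized in equal numbers" (13.1.3). Accrual over 15 months (13.1.3). Data review every 3 months (13.1.7), which the section does not tie to this rule.

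**Assumptions.** The true rates of related grade 4 and grade 5 events are not given, so a range is shown. Outcomes are treated as independent and known at each check.

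**1. Grade 5 left out.** For the early part, P(trigger) = 1 − Σ C(10,k) pᵏ(1−p)¹⁰⁻ᵏ over k = 0, 1, 2, where p is the rate of *countable* events. As written p is the grade 4 rate; with grade 5 counted it is the sum of the two.

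| Assumed grade 4 / grade 5 rate | As written | Grade 5 counted |
|---|---|---|
| 5% / 5% | 1.2% | 7.0% |
| 10% / 10% | 7.0% | 32.2% |
| 0% / 10% | 0% | 7.0% |
| 0% / 20% | 0% | 32.2% |

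The last two rows are extreme and only show the mechanism: related deaths alone can never trigger the rule. The worked case needs no assumed rate. Two grade 4 events plus one grade 5 gives a count of 2, below 3.

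**2. The two denominators.** The events needed are the smallest whole number at or above 0.3 × the denominator.

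- *Restarted at patient 11:* at patients 11, 12 and 13 the denominators are 1, 2 and 3, so one event (1/1, 1/2 or 1/3) suffices. Two suffice at denominators 4 to 6, and three at 7 to 10.
- *Cumulative:* 4 events in the arm are needed at n = 11 to 13, 6 at 20, 9 at 30 and 12 at 40.

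The chance of ever suspending an arm of 40, by exact patient-by-patient recursion and including the early part, is shown below. Quarterly looks are placed at 16, 24, 32 and 40 per arm because 80 patients in 15 months is 16 per quarter, or 8 per arm. The early part is evaluated at patient 10 in every column.

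| True rate of countable events | Every patient: restarted | Every patient: cumulative | Quarterly: restarted | Quarterly: cumulative |
|---|---|---|---|---|
| 5% | 16.1% | 1.2% | 4.4% | 1.2% |
| 10% | 35.6% | 8.0% | 18.0% | 7.4% |
| 20% | 74.7% | 42.3% | 60.2% | 38.4% |

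Most of the 16.1% comes from the tiny denominators. The early part gives 1.15% at a 5% rate, and any event in patients 11 to 13 adds (1 − 0.0115) × (1 − 0.95³) = 14.1%, for a total of 15.2%.

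**3. Does restarting hide toxicity?** No. With at most 2 events in the first 10 and fewer than 0.3m in the next m, the total is below 2 + 0.3m. That is less than 0.3 × (10 + m) = 3 + 0.3m. The restart can only trigger more often than the cumulative rule, never less.

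**The case against.** A reader might infer that treatment-related deaths could go unnoticed. The documents do not support that. Section 9.2 requires routine and expedited reporting of every on-study death whatever the cause, and 9.2.1 sets a 24-hour clock for grade 5 events. Section 13.1.7 adds three-monthly review and semi-annual DSMB reports, and 13.1.8 lets toxicity inform early termination. All of this stands, so the omission is confined to the formal rule. It still matters there, because none of those routes commits to pausing enrolment.

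A reader might also infer that a safe trial would be stopped. The action is a temporary pause for data review, not termination.

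On the denominator, the strongest reply is that 3/10 equals 30%, so the later part most naturally means the same threshold carried forward. A rule that fires on 1/1 is an unlikely intent. That is a good reason to prefer the cumulative reading, but the text does not say it.

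The larger suspension percentages also depend on checking after every patient, which the plan does not specify. Under quarterly looks the gap narrows, though it does not close.

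Finally, 13.1.3 reports 81 enrolled by November 2016, of whom 24 were ineligible. If the other 57 were all randomized, each arm already held about 28 patients, so the small-denominator problem may have passed by the time of this version. The grade 5 omission applies throughout accrual.

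**Conclusion.** The grade 5 omission holds on the wording alone. The trigger names grade 4, the protocol treats grade 5 as a separate grade elsewhere, and a related death therefore does not count towards the only pre-committed suspension rule. It is probably a drafting slip, but it should be corrected.

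The denominator point is secondary: a real ambiguity rather than a demonstrated error. Its size depends on the assumed toxicity rates and checking schedule. At a 10% true rate, the restarted and cumulative readings give 36% against 8% if checked after each patient, and 18% against 7% if checked about quarterly.

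It would be tempting to say that both changes simply make the rule safer at no cost. They pull in opposite directions. Counting grade 5 raises sensitivity. Choosing the cumulative denominator lowers it relative to the literal text, for example from 75% to 42% at a 20% true rate with checks after every patient.

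**What to change.** 1. In 13.1.7, make the qualifying event a grade 4 or 5 hematologic or non-hematologic toxicity at least possibly related to treatment. This changes a few words and needs no new data, since grade 5 events and their attribution are already collected. The cost is a slightly more sensitive trigger; the increase is material only if related deaths are not rare.
2. State whether the later 30% is taken over all patients randomized to the arm to date or only over those after the tenth. The cumulative form fits the 3-of-10 threshold best.
3. State when the rule is checked, and add a short table of suspension probabilities for the chosen reading and schedule. If the cumulative form is chosen, disclose that it is less sensitive than the literal text, so that the DSMB and CTEP accept that trade-off knowingly.

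The plan's own thresholds, attribution standard and action stay as they are.

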7.0 TREATMENT PLAN/INTERVENTION

Patients will be randomized with equal probability to receive daily treatment with Z-Endoxifen HCl or tamoxifen. Treatment on Arms I and II will continue until disease progression or unacceptable adverse event.

Protocol treatment is to begin \leq 14 days of registration/randomization in order to allow for Z-Endoxifen HCl to arrive for patients assigned to Arm I.

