12.4 Refuse to begin protocol treatment following randomization

If an eligible patient refuses to begin treatment following randomization (and is classified as a cancel by the Research Base), all on-study materials and the End of Active Treatment/Cancel Notification Form must be submitted. For those patients who also consent to the correlative studies, research biospecimens are not to be submitted. No further data submission is necessary. Future therapy is at the discretion of the treating physician.

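### The safety stopping rule in 13.1.7 counts patients randomised rather than patients who began treatment, which makes suspension slightly less likely than intended

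*Combined protocol and SAP*

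**What the plan says.** Section 13.1.7 applies a two-part rule to each arm separately. The first part is a count: "If 3 or more of the first 10 patients randomized to a given treatment arm". The second is a running proportion: "30% or more of patients randomized to that treatment arm thereafter develops a grade 4 hematologic or non-hematologic toxicity". In both parts the event must be "possibly, probably or definitely related to treatment, the enrollment to the trial will be temporarily suspended". The study team "will review the trial data every 3 months to identify accrual, toxicity, and endpoint problems".

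Other sections show that being randomised is not the same as being at risk:

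- Section 7.0 allows up to "14 days of registration/randomization in order to allow for Z-Endoxifen HCl to arrive for patients assigned to Arm I".
- Section 12.4 covers eligible patients who refuse to begin after randomisation, and for them "No further data submission is necessary". Section 12.5 says the same of patients found ineligible between randomisation and first dose.
- Section 13.1.3 makes an allowance that covers both ineligible patients and those who cancel before starting, without splitting the two.

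Elsewhere the statistical section uses a different population. Under 13.1, eligible, consented patients who "have begun treatment will be evaluable for assessment of all of the clinical endpoints". Section 13.1.6.2 divides the response rate by eligible patients who began treatment. Section 13.1.7 refers to neither.

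**The concern.** The numerator is treatment-related toxicity, which requires a dose. The denominator, and the list of the first 10, require only randomisation. A patient who never starts cannot enter the numerator but permanently takes one of the first 10 places and permanently enlarges the 30% denominator. A patient waiting for a first dose does the same for up to two weeks.

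Both effects make the observed proportion smaller than the proportion among patients exposed. The rule exists to pause enrolment while adverse events are examined, so the error runs toward not pausing. The plan would also be using one population for its clinical endpoints and another for its safety trigger without saying why.

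**Working it through.** **Starting point.** The plan gives no operating characteristics for the safety rule, so there is no figure of its own to reproduce. The inputs are 40 patients per arm over 15 months (13.1.3), first dose within 14 days of randomisation (7.0), adverse event assessment on day 1 of each 21-day cycle (5.1, 5.2), and review every 3 months (13.1.7). The never-start share is not stated, so 0%, 5% and 10% are assumed.

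**Step 1: patients waiting for a first dose.** Accrual per arm is 40 / (15 × 30.4375) = 0.0876 per day. With a mean wait of 7 days (assumed), 0.0876 × 7 = 0.61 patients are randomised but undosed at any time. With the full 14 days it is 0.0876 × 14 = 1.23. In the first-10 clause they only delay the count, because they eventually start.

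**Step 2: never-starters in the first-10 clause.** At a true rate of 30% per dosed patient, the chance of 3 or more events is:

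- 10 of 10 dosed: 1 − 0.7^10 − 10(0.3)(0.7^9) − 45(0.09)(0.7^8) = 61.7%
- 9 of 10 dosed: 1 − 0.7^9 − 9(0.3)(0.7^8) − 36(0.09)(0.7^7) = 53.7%

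Averaging over a never-start share q replaces 0.3 with 0.3(1 − q):

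- q = 5%: rate 0.285; 1 − 0.0349 − 0.1392 − 0.2497 = 57.6%
- q = 10%: rate 0.27; 1 − 0.0430 − 0.1590 − 0.2646 = 53.3%

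So this clause alone loses about 4 points at 5% and 8 points at 10%.

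**Step 3: never-starters in the 30% clause.** With n randomised and k never starting, the limit among dosed patients is 0.30 × n / (n − k). At n = 40:

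- k = 2: 12/38 = 31.6%
- k = 4: 12/36 = 33.3%

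**Step 4: both clauses together.** Simulation used 40 patients per arm, uniform accrual over 15 months, start delay uniform over 0 to 14 days, toxicity counted 21 days after start, 3-monthly looks during accrual, and the 30% clause read cumulatively once more than 10 are counted. Chance of suspension:

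| True rate | Never start | Randomised | Began treatment |
|---|---|---|---|
| 30% | 0% | about 73% | under 1 point higher |
| 30% | 5% | about 67% | about 73% |
| 30% | 10% | about 62% | about 72% |
| 20% | 5% | about 33% | about 37% |

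A repeat run of this setup agreed to within about two points. The differences at a 30% rate are in line with the exact losses in Step 2.

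**Step 5: also excluding dosed patients not yet assessed.** This moves the chance of suspension at a 30% rate by about 3 to 4 points more. With no never-starters, randomised against assessed gives 73% against 76% at a true 30% rate, and 95.4% against 96.3% at 40%.

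**The case against.** The best counter-argument is that the two clauses must be read together. The first-10 clause is an absolute count, so patients who are merely waiting cannot dilute it. Take 14 randomised with 4 events, the 2 newest not yet assessed: 4/14 = 28.6% does not suspend, while 4/12 = 33.3% would. But the four events lie among patients 1 to 12, and they escape the first-10 clause only if patients 11 and 12 both had one. That is C(10,2)/C(12,4) = 45/495 = 9% of arrangements. In the other 91% the trial is already suspended. This argument stands, and it removes most of the effect of waiting patients. It does not deal with never-starters, who use up places in the first 10 for good.

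A reader who looks at the 30% clause alone might infer that suspensions are often missed: simulated alone at a true 30% rate, the chance is about 61% on randomised patients against 71% on assessed patients. The documents do not support that reading, because the rule has two clauses and together they give 73% against 76%.

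It can also be said that 13.1 already governs, since adverse events are listed under secondary clinical endpoints (13.1.6.1). That is arguable, but 13.1.7 uses its own wording and makes no cross-reference. Most ineligible patients leave before randomisation (4.5), which keeps the number of never-starters down without removing them. Expedited reporting of grade 4 events (9.2.1), the 3-monthly reviews and the semi-annual DSMB reports also protect patients independently of this denominator.

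Finally, because the start window exists "in order to allow for Z-Endoxifen HCl to arrive for patients assigned to Arm I", a reader might infer a larger understatement in the experimental arm. Section 7.0 applies the window to both arms and no actual delays are given, so that does not follow.

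**Conclusion.** The wording is mismatched: the numerator needs exposure and the denominator does not. The direction is toward not suspending, and the size is modest. At a true 30% rate the loss is under 1 point if everyone starts, about 6 points (73 − 67) if 5% never start, and about 10 points (72 − 62) if 10% never start. These figures rest on assumed never-start shares, planned accrual, 3-monthly looks and a cumulative reading of the 30% clause. Slower accrual would leave fewer patients waiting at any time; it would not change the never-starter effect. The documents support neither a large understatement nor a difference between arms. This is a wording correction worth making, not a flaw that undermines safety monitoring.

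**What to change.** In both clauses of 13.1.7, replace patients randomized to with patients who began treatment on, and cross-refer to 13.1 so that the safety rule and the clinical endpoints start from the same exposed population. The change needs treatment start dates and no new type of data.

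The cost is slightly more suspension at acceptable rates: about 33% to 37% at a true 20% rate with 5% never starting. The consequence of a trigger is a temporary pause for review.

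A further requirement for a post-dose assessment is optional. It would count early events before event-free patients complete their window, and a one-cycle cut-off is debatable when treatment runs to progression. On the 30% clause alone, an assessed-patient denominator raises suspension at a true 20% rate from 16% to 27%. If it is adopted, the observation window and the operating characteristics of the whole rule should be stated with it.
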